# 9. Safety Analysis

Safety analyses will be performed using SAS population defined in Section 4.4. For each of the safety parameters, a summary statistic will be provided overall and by treatment group. All safety summaries will be descriptive and no statistical significance tests will be performed.

Safety and tolerability will be evaluated by all AEs, immediate AEs (30 minutes post-vaccination), solicited local and systemic AEs up to seven days post-vaccination, unsolicited AEs up to 28 days post-vaccination, SAEs, AESIs, MAAEs, NOCDs, AEs leading to discontinuation up to the end of the study, and deaths. In summary tables, only Treatment-Emergent AEs (TEAEs) will be counted. The clinical laboratory (haematology, chemistry, urinalysis), vital signs, and symptom-directed physical examination abnormalities will also be part of safety evaluation.

These tables will also be presented by prior influenza vaccination status, if >25% of the enrolled subjects have received a standard influenza vaccine during the 12 months prior to study vaccination to assess the secondary safety endpoints.

All safety data will be listed by subject.

### 9.1. Incidence of Adverse Events

An overall summary of the number and percentage of subjects will be presented for following categories:

- Immediate solicited and unsolicited AEs
- Immediate solicited AEs
- Immediate unsolicited AEs
- Solicited AEs:
  - Grade 3 or higher solicited AEs
  - Solicited local AEs
  - Solicited Systemic AEs

Medicago USA Page **34** of **55** 

Statistical Analysis Plan, Version 5.0

Date Issued: 14MAR2022

- Unsolicited AEs:
  - Related unsolicited AEs
  - o Grade 3 or higher unsolicited AEs
  - o Grade 3 or higher related unsolicited AEs
- Any SAE
- Any related SAE
- Any related Hypersensitivity reactions
- Any Potential Immune-Mediated Diseases (pIMDs) and other AESI
- Any related pIMDs and other AESI
- Any MAAE
- Any related MAAE
- Any NOCD
- Any related NOCD
- Any AE leading to discontinuation
- Any related AE leading to discontinuation
- Any AE leading to deaths
- Any related AE leading to deaths
- Any clinically significant lab data

### 9.2. Solicited Adverse Events

Subjects will be monitored for both solicited local AEs (erythema, swelling, and pain at the injection site) and solicited systemic AEs (fever, headache, fatigue, muscle aches, joint aches, chills, a feeling of general discomfort, swelling in the axilla, and swelling in the neck) from the time of vaccination through Day 7 post dose. The causal relationship of all solicited local and systemic AEs will be considered related.

Table 2: Intensity Grades for Solicited Local and Systemic AEs

Symptoms	Intensity				
	None	Grade 1 (Mild)	Grade 2 (Moderate)	Grade 3 (Severe)	Grade 4 (Potentially life- threatening)
Injection Site AEs (I	Local AEs)				
Erythema (redness)	< 25 mm	25 - 50 mm	51 - 100 mm	> 100 mm	Necrosis or exfoliative dermatitis
Swelling	< 25 mm			> 100 mm or prevents daily activity	Necrosis

Medicago USA Page 35 of 55

Symptoms	Intensity					
	None	Grade 1 (Mild)	Grade 2 (Moderate)	Grade 3 (Severe)	Grade 4 (Potentially life- threatening)	
Pain	None			narcotic pain	room (ER) or	
Solicited Systemic A	Es					
Fever (°C or °F)	< 38.0 °C < 100.4 °F	38.0 - 38.4 °C 100.4 - 101.1 °F	38.5 - 38.9 °C 101.2 - 102.0 °F	39.0 - 40.0 °C 102.1 - 104.0 °F	> 40.0 °C > 104.0 °F	
Headache	None	No interference with activity	Repeated use of non-narcotic pain reliever for more than 24 hours or some interference with activity	use of narcotic pain reliever or prevents daily	Results in a visit to emergency room (ER) or hospitalization	
Fatigue	None	No interference with activity	Some interference with activity	Significant; prevents daily activity	Results in a visit to emergency room (ER) or hospitalization	
Muscle aches	None	No interference with activity	Some interference with activity	Significant; prevents daily activity	Results in a visit to emergency room (ER) or hospitalization	
Joint aches, chills, feeling of general discomfort or uneasiness (malaise), swelling in the axilla, swelling in the neck	None	No interference with activity	Some interference with activity not requiring medical intervention	activity and		

For following timepoints, the number and percentage of subjects will be summarized for each solicited AE, intensity grade, and treatment group as a whole:

- 30 min post-dose;
- Up to 7th day post-dose.

E-diary is considered to be the principal system to be used to collected solicited adverse events. Paper diary could be used as back-up. In the event that both an e-diary and a paper diary were completed by the subject for the same solicited AE and the same timepoint, the record with the PI assessment will be used for analysis; otherwise, the higher grade will be used in the analysis.

Immediate solicited AE and all solicited AE up to 7 days information will specifically be presented by gender (Both, Male and Female), race (All, Caucasian or White; Black or

Medicago USA Page **36** of **55** 

African American; Asian) and prior vaccine status (Both, Yes and No), if >25% of the enrolled subjects have received a standard influenza vaccine during the 12 months prior to study vaccination, for the overall population (65 years of age and older).

Solicited local and systemic AE data including specific details will be presented in listings.

#### 9.3. Unsolicited Adverse Events

An adverse event (AE) is defined as any untoward medical occurrence in a subject or clinical investigation subject who was administered a pharmaceutical product, with or without a causal relationship with the treatment.

For the purpose of inclusion in AE tables, incomplete data will be imputed based on section 4.3. Subsequently, AEs might be reclassified as medical history based on the rules described in the same section.

All AEs will be classified by System Organ Class (SOC) and Preferred Term (PT) according to the Medical Dictionary for Regulatory Activities (MedDRA, version 23.1 or later).

Summaries of the number and percentage of subjects with AEs will be provided by SOC (in internationally agreed order) and PT (in alphabetical order) separately. At each level of subject summarization, a subject is counted once if the subject reported 1 or more events.

Percentages will be calculated out of the number of subjects in the SAS population.

Subjects with at least 1 AE will be summarized by treatment group as a whole.

For the following categories, AE information will specifically be presented by gender (Both, Male and Female), race (All, Caucasian or White; Black or African American; Asian) and prior vaccine status (Both, Yes and No), if >25% of the enrolled subjects have received a standard influenza vaccine during the 12 months prior to study vaccination, for the overall population (65 years of age and older):

- Unsolicited AEs for 28 days following study vaccine administration;
- Immediate unsolicited AEs up to 30 minutes after vaccination;
- SAEs;
- Related Hypersensitivity Reactions (AESI);
- Narcolepsy
- pIMDs and Other AESI;
- MAAEs;
- NOCD;
- AEs leading to study discontinuation;
- AEs leading to death;
- Most frequent (defined as  $\geq 1.0$  % of subjects in one of AdjQVLP treatment groups) unsolicited AEs within 28 days after vaccination.

Subject AE data including specific details will be presented in listings.

Medicago USA Page 37 of 55

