When count data are presented, the percentage will be suppressed when the count is zero in order to draw attention to the non-zero counts. A row denoted "Missing" will be included in count tabulations where specified on the shells to account for dropouts and missing values. The denominator for all percentages will be the number of subjects in that clinical diagnosis category within the analysis set of interest, unless otherwise specified.

Baseline value is defined as the last non-missing data on or before the IM injection of the study vaccine, unless otherwise specified.

Study Day is the number of days since the administration of the study vaccine, which is counted as Study Day 0. If the assessment date is after the date of the vaccination, the study day is calculated as date of assessment - date of the vaccination + 1. If the assessment date is prior to the date of the vaccination, the study day is calculated as date of assessment - date of the vaccination.

Medicago USA Page 17 of 55

Onset day is calculated as date of event – date of the vaccination +1.

During the programming period, the table/listing/figure shell format and footnote might be edited. And this kind of change is not be considered as analysis changes or impact the analysis results.

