# 4.1. Sample Size

No statistical sample size calculations were performed. The determined sample size up to approximately 120 subjects with 40 subjects in each treatment group will make it possible to perform the initial evaluation of vaccine immunogenicity and detect sizable differences in rates of adverse events since objective of this study is to quantify the type, percentage, intensity, duration, and relationship of common post-vaccination safety events to determine if they differ clinically among the treatment groups.

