### 4.4.2. Safety Analysis Set (SAS)

The SAS is defined as all subjects who received either the adjuvanted QVLP or the active comparators. All safety analysis will be performed using the SAS, according to the treatment the subjects actually received.

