# 5. Subject Disposition

Subject disposition will be summarized for each treatment group and total for subjects in All Screened Set. Tables will indicate the number of subjects who were enrolled into the study, the number of subjects who are vaccinated, the number of subjects in each analysis set, the number of subjects who completed Day 28, Day 182 and the entire study, and the number of subjects who prematurely discontinued study for any of, but not limited to, the following reasons:

- Adverse event.
- Death
- Lost to follow-up
- Physician decision
- Protocol violation
- Screen failure
- Screen failure-enrollment closed
- Trial site terminated by sponsor
- Study terminated by sponsor
- Subject withdrew consent
- other

In addition, in case of the third interim analysis, the frequency and percentage of subjects who are ongoing at the data cut time will also be summarized.

Subject disposition data (including subject identifier, date of completion/early discontinuation and, for those who discontinued early, the specific reason(s) for discontinuation) will be presented in a listing. In listings, data for all screened subjects will be presented, including those who were not randomized (e.g., screening failures).

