#### 9.3.3. Serious Adverse Events

An SAE is any untoward medical occurrence (whether considered to be related to the study vaccine or not) that, at any dose:

- Results in death;
- Is life-threatening (at the time of the event);

Note: the term "life-threatening" in the definition of an SAE refers to an event that put the subject at risk of death at the time of the event; it does not refer to an event that hypothetically might have caused death if it were more severe;

- Requires inpatient hospitalization (≥ 24 hours) or prolongation of existing hospitalization (elective hospitalizations/procedures for pre-existing conditions that have not worsened are excluded);
- Results in persistent or significant disability/incapacity;
- Is a congenital abnormality/birth defect;
- Is another medically important event.

In addition to being presented by gender (Both, Male and Female), race (All, Caucasian or White; Black or African American; Asian) and prior vaccine status (Both, Yes and No), if >25% of the enrolled subjects have received a standard influenza vaccine during the 12 months prior to study vaccination, for the overall population (65 years of age and older) as indicated in section 9.1, summaries of the number and percentage of subjects with at least one SAE will be presented by SOC and PT for following time period separately (based on AE analysis start date):

• from Day 1 up to Day 28;

Confidential

Medicago USA Page 38 of 55

- from Day 29 up to Day 182;
- from Day 183 up to the end of study (Day 365).

At each level of subject summarization, a subject is counted once if the subject reported 1 or more events.

All SAEs will be presented in a listing separately. If there are no SAEs at the end of the study, the tables or listings will state that there are no SAEs in the study.

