#### 10. Interim Analysis

Interim analyses will be performed (i) after Day 28 HI data available as of the Feb. 12, 2021 data transfer, (ii) after the last subject has completed Day 28 assessments and (iii) after the last subject has completed Day 182 assessments.

The first interim analysis based on Day 28 HI data available as of the Feb. 12, 2021 data transfer will inform a business decision to confirm the vaccine formulation for a Phase 2/3 study for AdjQVLP and will include immunogenicity analyses for HI Antibody Response against Homologous Influenza Strains (GMT, GMFR and SC and SP rate analyses).

The second interim analysis will include all tables.

The third interim analyses at Day 182 will be a full interim analysis with all tables/listings/figures planned for the final analysis.

The results of the interim analyses will be confidential and strictly limited to the authorized staff members and will allow discussions of the clinical data to inform study design decisions of the subsequent study, without having to wait until after the end of the follow-up period for study completion. No adjustments to the final analyses as a result of these interim analyses were therefore deemed necessary.

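### Late-window safety percentages divide by everyone vaccinated, so subjects lost before a window, or not yet fully observed at an interim, count as event-free

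*SAP*

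**What the plan says.** SAP 9.3 states the rule for adverse event tables: "Percentages will be calculated out of the number of subjects in the SAS population". SAP 4.4.2 puts no follow-up condition on that set: "The SAS is defined as all subjects who received either the adjuvanted QVLP or the active comparators". The general default in SAP 4 leads to the same place: "The denominator for all percentages will be the number of subjects in that clinical diagnosis category within the analysis set of interest, unless otherwise specified".

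SAP 9.3.3 to 9.3.8 tabulate SAEs, AESIs, MAAEs, NOCDs, AEs leading to discontinuation and AEs leading to death as numbers and percentages of subjects. There are three windows: up to Day 28, then "from Day 29 up to Day 182", then "from Day 183 up to the end of study (Day 365"). SAP 3.2.1 lists these occurrences by window as primary safety endpoints. None of these sections gives a window-specific denominator, a person-time rate or a censoring rule.

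SAP 10 places the second interim after the last subject's Day 28 and the third after the last subject's Day 182. Of the second it says: "The second interim analysis will include all tables". The third is to contain every output planned for the final analysis. SAP 5 adds a count of subjects still in follow-up only "in case of the third interim analysis, the frequency and percentage of subjects who are ongoing at the data cut time".

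**The concern.** A subject last contacted on Day 20 cannot contribute an event to either later window, yet stays in both denominators. At an interim the same happens to someone who is still in the study but has spent only a few days in the window. In both cases, absence of observation is printed as absence of an event.

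These are primary safety endpoints. SAP 10 says the interim results will inform the design of the subsequent study, and SAP 11 says the full Day 28 interim will be shared with FDA. SAP 4 also suppresses the percentage when a count is zero, so a window that nobody has entered prints the same bare zero as a window fully observed without events.

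**Working it through.** The documents give no late event rate and no dropout rate, and SAP 4.1 says no sample size calculation was done. There is therefore no stated figure to reproduce beyond 3 x 40 = 120. What can be checked is how the denominator rule behaves.

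**Inputs**
- N = 40 planned per arm (SAP 4.1: "approximately 120 subjects with 40 subjects in each treatment group").
- Window lengths (SAP 9.3.3): 182 - 29 + 1 = 154 days and 365 - 183 + 1 = 183 days.
- Share lost before a window, d: not documented; 0-20% assumed.
- Subjects with an event, x: not documented; 1 and 4 used for illustration.
- Enrolment of about 4 to 5 months (Protocol synopsis, planned study period). Uniform accrual is assumed, with 30.44 days per month, so E = 121.8 or 152.2 days.

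**Final analysis.** Printed percentage = x/N. Percentage among those still followed at window start = x/[N(1 - d)]. Their ratio is 1 - d, so the relative understatement equals d.

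| d | Followed at start | 1 event: printed / at risk | 4 events: printed / at risk |
|---|---|---|---|
| 0% | 40 | 2.5% / 2.5% | 10.0% / 10.0% |
| 5% | 38 | 2.5% / 2.6% | 10.0% / 10.5% |
| 10% | 36 | 2.5% / 2.8% | 10.0% / 11.1% |
| 15% | 34 | 2.5% / 2.9% | 10.0% / 11.8% |
| 20% | 32 | 2.5% / 3.1% | 10.0% / 12.5% |

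For scale, the exact (Clopper-Pearson) 95% interval for 4/40 is 2.8% to 23.7%.

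**Between arms.** If two arms have equal rates among those followed but lose shares dA and dB, the printed ratio is (1 - dB)/(1 - dA). This gives 1.00 for 10% and 10%, 0.85/0.95 = 0.895 for 5% and 15%, and 0.80 for 0% and 20%.

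**Interims.** A subject vaccinated u days before the last one has 28 + u days of follow-up at the second interim and 182 + u at the third, with u uniform from 0 to E. Because E is shorter than either window, u is also the time spent in the window that has just opened, and its mean is E/2.
- Second interim, Days 29-182: 60.9/154 = 39.5% (4 months) or 76.1/154 = 49.4% (5 months) of person-time observed. Longest follow-up is 28 + 122 = 150 or 28 + 152 = 180 days, so nobody has finished this window and none of Days 183-365 has been observed.
- Third interim, Days 183-365: 60.9/183 = 33.3% or 76.1/183 = 41.6% observed. Longest follow-up is 304 or 334 days, so nobody has reached Day 365.

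**Other provisions.** SAP 4.3 treats missing values as missing, but an event that was never reported leaves no missing record. The row for missing values in SAP 4 appears only where the table shells call for it, and it does not alter N. Neither removes an unobserved subject from the denominator.

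**Stopped arms.** SAP 4 analyses the five stopped groups like the others, and SAP 4.2.1 sends everyone enrolled after protocol version 4.0 into the three continuing arms. At an interim cut the continuing arms therefore include the most recently vaccinated subjects, and follow-up can differ between stopped and continuing arms. This alone does not distort comparisons among the three continuing arms.

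**The case against.** Crude incidence over all vaccinated subjects is a common convention, and SAP 9 makes all safety summaries descriptive, with no tests. SAP 5 already tabulates by arm the numbers completing Day 28, Day 182 and the study, and counts and listings accompany every percentage, so a careful reader could approximate the correction. Protocol 11.3.1 follows all vaccinated subjects to the end of the study if they allow it, and with a single dose there is no treatment course to abandon. All of this stands. It limits the size of the problem but does not change the printed denominator.

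A reader might go further and infer that late rates are understated whatever happens, or that an arm losing more subjects to early reactions would look safer later. The documents do not support either. With no loss, the final percentages are unaffected. No dropout rate is given, let alone one that differs by arm. The only related figure is 15 QVLP subjects withdrawn for treatment-emergent events across eight earlier trials, all aged 65 or older on 30 µg/strain (Protocol 1.3.1). Set against the 6352 such subjects in Protocol 1.3, that is 15/6352, or about 0.24%. It reflects unadjuvanted experience and omits other losses, but it gives no ground for expecting large reaction-driven dropout.

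A further objection concerns the remedy. A window-start denominator still counts a subject who entered the window one day before the cut, or who left midway, as fully observed. This is correct, and it matters at the interims: the cuts follow the last subject's Day 28 and Day 182, so nearly everyone has just entered the newly opened window. A different remedy is needed there. Comparing only those still followed also departs from the randomised groups, which is a reason to keep the full-set percentage in the overview.

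**Conclusion.** The point holds as a matter of how the tables are defined. At the final analysis its size is conditional and probably small: zero without loss, 0.1 to 0.6 points for 1 event in 40 and 0.5 to 2.5 points for 4 in 40 at an assumed 5-20% loss, well inside the sampling uncertainty of a 40-subject arm. At the second and third interims it does not depend on dropout: less than half of the newly opened window's person-time is observed under the accrual assumption, and at the second interim the last window is not observed at all. Those shares rest on the planned 4-5 month enrolment and uniform accrual; the documents give no data cut dates for these two interims, and slower or uneven enrolment would change them. This is a cheap improvement, not a flaw that threatens the study's conclusions.

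**What to change.** In SAP 9.3.3 to 9.3.8, for the Day 29-182 and Day 183-365 tables, take as denominator the safety-set subjects still in safety follow-up on the window's first day, and print that N in each column. Define follow-up by last safety contact, not withdrawal status, so that events reported after withdrawal under Protocol 11.3.1 stay matched to their denominator. Do not restrict to subjects who completed the window, because that would drop those who had an event and then left. Keep full-set percentages for the cumulative overview.

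In SAP 10, for the second and third interims, also report events per person-time observed in the window, or else flag or suppress any window not fully observed.

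The cost is a few sentences and a window-specific N derived from last-contact and disposition dates. Column Ns will differ between windows, and late percentages will rise slightly if subjects have been lost.
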